4.3 Inclusion/Exclusion Criteria

Inclusion criteria:

1. Diagnosis of ACS defined as a new pulmonary infiltrate involving at least one segment of the lung on a chest x-ray or chest CT scan with 2 or more of the following: chest pain, tachypnea (defined as a respiratory rate greater than 20 breaths per minute), dyspnea, cough, hypoxemia (see 3.3 Data Collection and Statistical Considerations for definition of hypoxemia), or body temperature greater than or equal to 38.0 degrees Celsius.

2. Hemoglobin electrophoresis confirming (HbSS, SC, or S β^0) (historical records sufficient).

3. Age greater than or equal to 18.

Exclusion Criteria:

1. Any absolute contraindication to heparin, including known bleeding diathesis, history of HIT, or history of an allergic reaction.

2. Platelet count less than 50 per microliter (current admission).

3. Historical diagnosis of moyamoya disease as documented in medical records.

4. Historical diagnosis of proliferative retinopathy as documented in medical records.

5. Current participation in a chronic exchange transfusion program.

6. Underlying hypercoagulable disorder other than SCD.

7. Currently receiving therapeutic anticoagulation.

8. Currently receiving antiplatelet agents.

9. Currently receiving estrogen containing oral contraceptives.

10. Chest CT scan documented PE performed as standard of care prior to study enrollment (current admission).

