
Potential adverse events include heparin-associated risks, such as allergic reaction, major bleeding, minor bleeding, thrombocytopenia, and heparin induced thrombocytopenia (HIT), or any other adverse reaction suspected secondary to drug administration. All subjects enrolled in the study and received any UFH will be included in the safety evaluation.

A member of the research staff will collect the study data. All data required by the study protocol will be documented in the inpatient electronic medical record system. De-identified subject information will be written on Case Report Forms (CRFs) and all data collected will be stored in locked files at the Hemophilia Center of Western Pennsylvania (HCWP). Additionally, data will be entered into research electronic capture (REDCap) and compared to ensure consistency. No personal identifiers will be associated with the data. The Institutional Review Board (IRB) may inspect records at any time.

A sample size of 20 subjects for the pilot study is based on clinical rather than statistical considerations and should provide a preliminary estimate of primary and secondary clinical outcomes and assess prespecified feasibility criteria as detailed above. Based on 75,000 to 100,000 African Americans with SCD in the United States who develop ACS at a frequency of 8.8 per 100 patient years, with 50% developing ACS at some point during his or her lifetime, and given the fact that approximately 30 patients are admitted annually at UPMC hospitals (Presbyterian, Montefiore, Magee, Shadyside) with ACS, we estimate that at least 80%, or 24 patients per year, will meet inclusion and exclusion criteria, and expect to enroll 10 patients, or slightly less than 50% per year, which should meet the n=20 subjects required for the pilot study.^{3,4} This is a pilot feasibility study, so comparisons will be descriptive, including frequencies and percentages for categorical variables and mean, median, range, and standard deviation for continuous variables.

Demographics and medical information will be summarized with descriptive statistics as well. Adverse events will be summarized by frequency, relatedness, and severity.

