4.0 Human Subjects

4.1 General Characteristics – Minority Inclusion and Non-Discriminatory Statements

Adult patients with SCD (HbSS, SC, or S β^0) aged 18 years or older admitted to UPMC (Presbyterian, Montefiore, Magee, Shadyside) hospitals with a diagnosis of ACS will be eligible for screening to participate in the trial. Children and pregnant females will not be enrolled in the study. Any patient with a predisposition towards thrombosis, other than SCD, and bleeding, as detailed in the inclusion and exclusion criteria, will be excluded from study participation. Specifically, moyamoya disease has a 20% incidence of intracranial hemorrhage in adults in the United States.¹⁶ The incidence of the disease is 1 in 1 million in the United States; therefore, even with an increased association between moyamoya disease and SCD, it is unlikely to affect patient recruitment.¹⁶ Additionally, proliferative retinopathy predisposes towards vitreous hemorrhages with visual loss; however, the incidence of the disease is 0.5 per 100 patients, which, again, will be unlikely to affect patient recruitment.¹⁷

As SCD is an autosomal recessive disorder that predominantly affects individuals of African descent, it is anticipated that the study population will be comprised largely of African Americans, and the percentage of male and female participants will be similar in number. There will be no discrimination based on gender, race, or ethnicity. The gender, racial, and ethnic characteristics of the proposed study population will reflect the demographics of the disease, the city of Pittsburgh and surrounding areas, and UPMC. Written informed consent will be obtained from all subjects prior to enrollment in the study.

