Heparin therapy, like any other form of anticoagulation, increases the risk of bleeding. The risk of bleeding with UFH varies among clinical settings. The risk of bleeding with intravenous UFH in acute VTE is less than 3%.²⁰ Bleeding may be major, defined as a decrease in hemoglobin 2 grams per deciliter or more; transfusion of 2 or more units of red blood cells; or bleeding in a critical organ, such as intracranial, intraspinal, intraocular, pericardial, or retroperitoneal.²¹ The presence of major bleeding will result in the permanent discontinuation of UFH. If major bleeding occurs, protamine will be administered to reverse the anticoagulant effects of heparin. Protamine may result in hypotension, bradycardia, dyspnea, flushing, feeling of warmth, nausea, vomiting, or rarely anaphylaxis.¹⁴ Other medical interventions, such as intravenous fluids and red blood cell transfusions, will be administered as deemed appropriate. Minor bleeding is defined as all bleeding episodes that do not meet criteria for major bleeding. The treatment of minor bleeding may vary and will be determined by the specific clinical scenario. The decision to discontinue UFH in the setting of minor bleeding, permanently or only for a brief period of time, will be at the investigator's discretion. A known history of a bleeding diathesis will result in exclusion from study participation.

3. Thrombocytopenia

The risk of non-immune related thrombocytopenia with heparin varies anywhere between 5 and 30%.²² Thrombocytopenia will be defined as a platelet count less than 100,000 per microliter. UFH will be discontinued if the platelet count is less than 50,000 per microliter and may be resumed if the platelet count increases to greater than 50,000 per microliter during the study period. A baseline platelet count less than 50,000 per microliter will result in exclusion from study participation.

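### The platelet-count exclusion is 50 per microliter in section 4.3 but 50,000 per microliter in section 4.4, so the eligibility list as written excludes almost no one on platelet count

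*Combined protocol and SAP*

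**What the plan says.** Two places in the protocol exclude patients on the platelet count at entry.

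- Section 4.3, exclusion criterion 2: "Platelet count less than 50 per microliter (current admission".
- Section 4.4, under thrombocytopenia: "A baseline platelet count less than 50,000 per microliter will result in exclusion from study participation".

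The same paragraph of section 4.4 gives two further platelet limits. The first is a definition: "Thrombocytopenia will be defined as a platelet count less than 100,000 per microliter". The second is an on-study rule: "UFH will be discontinued if the platelet count is less than 50,000 per microliter".

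Three other passages show how the eligibility list is used. Section 3.2 makes randomization depend on meeting the inclusion and exclusion criteria. Section 4.1 relies on those criteria for patients predisposed to bleeding, who, "as detailed in the inclusion and exclusion criteria, will be excluded from study participation". Section 4.2 has research staff complete a screening assessment after consent and document every reason for exclusion.

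**The concern.** Both statements concern the count before treatment and both are per microliter, so they should agree. Section 4.3 is the formal eligibility list, and its figure is the far less restrictive of the two.

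This is a safety threshold for entry to a trial in which half the patients receive a heparin bolus and continuous infusion. A severely thrombocytopenic patient could satisfy criterion 2, be assigned to Arm A, and already be below the count at which section 4.4 stops the drug.

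There is a secondary issue for the pilot's own endpoints. Section 3.3 sets feasibility criteria on the proportion of potential participants excluded (below 20%) and on proper administration of study drug (at least 90%). With two thresholds in force, the same patient can be counted as eligible or as excluded.

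**Working it through.** No formula in the plan produces either threshold, so there is no derived figure to reproduce. The check is a side-by-side comparison in a common unit.

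| Rule | Section | Platelets per microliter |
|---|---|---|
| Exclusion at entry | 4.3, criterion 2 | below 50 |
| Exclusion at entry | 4.4, thrombocytopenia | below 50,000 |
| UFH discontinued | 4.4, thrombocytopenia | below 50,000 |
| Definition of thrombocytopenia | 4.4, thrombocytopenia | below 100,000 |

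**Size of the discrepancy**

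- Ratio of the two entry thresholds: 50,000 / 50 = 1,000.
- Section 4.3 threshold against the UFH discontinuation limit: 50 / 50,000 = 0.1%.
- Section 4.3 threshold against the thrombocytopenia limit: 50 / 100,000 = 0.05%.

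**Consequence by baseline count**

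- Below 50: excluded under both sections.
- 50 to 49,999: passes criterion 2 in section 4.3, excluded under section 4.4, and already in the range where section 4.4 stops UFH.
- 50,000 or more: not excluded on platelet count under either section.

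The two sections therefore disagree over almost the whole range below 50,000.

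**Does another exclusion close the gap?** The nearest is criterion 1: "Any absolute contraindication to heparin, including known bleeding diathesis, history of HIT, or history of an allergic reaction". It could remove some patients with low platelets, but on history or diagnosis; it contains no platelet count. No other item in the list refers to platelet count.

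**Feasibility rates.** The documents give no platelet distribution, so the number of patients affected cannot be estimated. What can be shown is the weight of one patient:

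- Section 4.2 allocates 10 patients to heparin. If administration is scored per patient, which is an assumption because section 3.3 does not say, one patient is 1 / 10 = 10% of the arm. That uses up the whole margin allowed by the 90% criterion.
- Section 3.3 expects about 30 admissions a year and 10 enrolments a year, so 20 patients take 20 / 10 = 2 years and about 60 admissions. If the exclusion rate is taken over all admissions, also an assumption, one reclassified patient moves it by 1 / 60 = 1.7 percentage points.

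These figures show sensitivity to one patient. They do not predict that any patient will be affected.

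**Sample size.** It does not depend on the threshold: "A sample size of 20 subjects for the pilot study is based on clinical rather than statistical considerations".

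**The case against.** The strongest reply is that this is an evident slip, a dropped 000 or a unit error, which any clinician would read correctly. Section 3.3 has a similar oddity, with leukocytosis defined as more than 10,000 white cells per liter. On this view the protocol as a whole still protects the patient. Section 4.4 is current text and states both the exclusion and the stopping rule at 50,000, and section 3.3 requires daily platelet counts in patients on UFH. For harm to occur, staff would have to apply 50 literally, overlook section 4.4, and start a drug that section 4.4 says to stop at that count. Nothing in the documents says that section 4.3 overrides section 4.4, and the screening form is not among the documents, so the threshold it carries is unknown.

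Much of this stands. The protocol contradicts itself; it does not lack a safeguard. The claim that criterion 2 excludes almost no one applies to the section 4.3 list alone, and it is a judgement resting on the protocol's own limits of 50,000 and 100,000. The likelihood of harm is not established. The effect on the feasibility rates is only possible: section 3.1 measures adherence in hours without infusion, setting aside stops made under institutional guidelines, and it is not clear whether a platelet-driven stop would count.

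None of it removes the contradiction. That the slip is easy to recognise makes it easy to correct, but an entry criterion for therapeutic anticoagulation should not depend on staff overriding the written text.

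**Conclusion.** The concern holds. Sections 4.3 and 4.4 state the same platelet exclusion 1,000-fold apart, in the same unit and in current text, with nothing to reconcile them. Taken literally, criterion 2 admits patients with counts from 50 to 49,999 per microliter whom section 4.4 excludes and for whom it discontinues UFH.

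This rests on two readings: that the count from the current admission in section 4.3 and the baseline count in section 4.4 are the same measurement, and that screening works from the section 4.3 list, as sections 3.2 and 4.1 indicate. The feasibility rates could be affected, by an amount the documents do not allow one to estimate.

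This is an internal inconsistency in a safety criterion, not a calculation error. It should be corrected before the criteria are applied.

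**What to change.** Reconcile exclusion criterion 2 in section 4.3 with the thrombocytopenia paragraph of section 4.4, so that a single platelet threshold in a single unit appears in both. The sponsor must confirm the figure; this review does not choose it. Check any screening form or CRF against the reconciled text. If patients have already been screened, check their recorded counts and reasons for exclusion against the confirmed threshold before reporting the feasibility rates.

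The cost is a one-line protocol correction and a check of the form, with no additional patients and no change to the analysis.

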4.4 Risk/Benefit Ratio

Risk of blood drawing

There may be discomfort with drawing blood, which may include pain, lightheadedness, dizziness, syncope, ecchymosis, bleeding, or infection in the tissue surrounding the vein. Appropriate medical intervention may consist of applying pressure to resolve bleeding or antibiotics in the setting of infection.

Risk of peripheral intravenous catheter placement

There may be discomfort with peripheral intravenous catheter placement, which may include pain, ecchymosis, bleeding, thrombophlebitis, or infection in the tissue surrounding the vein. Appropriate medical intervention may consist of applying pressure to resolve bleeding or antibiotics in the setting of infection.

Heparin associated risks

1. Allergic reaction

Allergic reactions are rarely reported with the use of intravenous UFH.¹⁸ Because of this, the exact incidence is unknown, but expected to be rare.¹⁸ Adverse events will be classified using the Common Terminology Criteria for Adverse Events (CTCAE) system, volume 4.03, 2010.¹⁹ Allergic type symptoms may include fever, chills, pruritis, rash, urticaria, paresthesias, chest pain, dyspnea, wheezing, nausea, vomiting, edema, tachycardia, hypotension, anaphylaxis, or death. Subjects will be monitored for the development of these symptoms. If these symptoms occur, and are felt to be the result of UFH, the infusion will be discontinued, and diphenhydramine, methylprednisolone, or other appropriate medical interventions will be administered. Anaphylaxis will result in the permanent discontinuation of UFH. The decision to permanently discontinue UFH

in less severe, or minor, allergic reactions will be at the discretion of the investigator. A known history of an allergic reaction to heparin will result in exclusion from study participation.

2. Bleeding

Heparin therapy, like any other form of anticoagulation, increases the risk of bleeding. The risk of bleeding with UFH varies among clinical settings. The risk of bleeding with intravenous UFH in acute VTE is less than 3%.²⁰ Bleeding may be major, defined as a decrease in hemoglobin 2 grams per deciliter or more; transfusion of 2 or more units of red blood cells; or bleeding in a critical organ, such as intracranial, intraspinal, intraocular, pericardial, or retroperitoneal.²¹ The presence of major bleeding will result in the permanent discontinuation of UFH. If major bleeding occurs, protamine will be administered to reverse the anticoagulant effects of heparin. Protamine may result in hypotension, bradycardia, dyspnea, flushing, feeling of warmth, nausea, vomiting, or rarely anaphylaxis.¹⁴ Other medical interventions, such as intravenous fluids and red blood cell transfusions, will be administered as deemed appropriate. Minor bleeding is defined as all bleeding episodes that do not meet criteria for major bleeding. The treatment of minor bleeding may vary and will be determined by the specific clinical scenario. The decision to discontinue UFH in the setting of minor bleeding, permanently or only for a brief period of time, will be at the investigator's discretion. A known history of a bleeding diathesis will result in exclusion from study participation.

3. Thrombocytopenia

The risk of non-immune related thrombocytopenia with heparin varies anywhere between 5 and 30%.²² Thrombocytopenia will be defined as a platelet count less than 100,000 per microliter. UFH will be discontinued if the platelet count is less than 50,000 per microliter and may be resumed if the platelet count increases to greater than 50,000 per microliter during the study period. A baseline platelet count less than 50,000 per microliter will result in exclusion from study participation.

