- If the anti-Xa UFH level is 0.30 to 0.70 units per milliliter, or therapeutic, no changes are necessary. Once a therapeutic anti-Xa UFH level is obtained, an anti-Xa UFH level will be repeated every 6 hours until two consecutive therapeutic results are achieved at which time the anti-Xa UFH level can be checked daily.
- If the anti-Xa UFH level is 0.71 to 0.80 units per milliliter, the rate of the infusion will be decreased by 2 units per kilogram per hour. A repeat anti-Xa UFH level will be checked 6 hours after the change in the infusion rate.
- If the anti-Xa UFH level is 0.81 to 1.00 units per milliliter, the infusion will be held for 1 hour then restarted after decreasing the rate of infusion by 3 units per kilogram per hour followed by a repeat anti-Xa UFH level in 2 hours.
- If the anti-Xa UFH level greater than 1.00 units per milliliter, the infusion will be held for 2 hours then restarted after decreasing the rate of infusion by 4 units per kilogram per hour followed by a repeat anti-Xa UFH level in 2 hours.

In the event of major bleeding, the anticoagulation effects of heparin will be reversed with protamine sulfate, a cationic protein that binds to heparin forming an ionic complex that neutralizes the anticoagulant effects of heparin.¹⁴ Protamine will be administered according to institutional guidelines¹⁵. The maximum protamine dose is not to exceed 50 mg and no more than 50 mg is to be given over 10 minutes. Protamine will be given by slow intravenous infusion via a peripheral intravenous catheter, or central venous access device if already present, per treating physician preference, over 10 minutes to minimize the risk of hypotension, bradycardia, dyspnea, flushing, feeling of warmth, nausea, vomiting, or rarely anaphylaxis.¹⁴ If a heparin bolus

was given within 2 hours of bleeding, protamine 1 mg per 100 units of heparin bolus will be administered. If no heparin bolus was given in the preceding 2 hours then the following protocol will be followed:

- If the heparin infusion, prior to bleeding, was less than 600 units per hours then 10 mg of protamine will be given.
- If the heparin infusion was 600 to 800 units per hour then 15 mg of protamine will be given.
- If the heparin infusion was 801 to 1100 units per hour then 20 mg of protamine will be given.
- If the heparin infusion was 1101 to 1400 units per hour then 25 mg of protamine will be given.

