Further data collected will include information regarding standard of care therapy (collected daily during duration of study), demographics (collected following study enrollment and screening), and medical information (collected following study enrollment and screening). Regarding standard of care therapy, data collected will consist of whether or not intravenous fluids were given; whether or not antibiotics were administered, number of antibiotics received, and class of antibiotics given (penicillin, cephalosporin, macrolide, fluoroquinolone, vancomycin, other); whether or not supplemental oxygen was received with documentation of need for noninvasive positive pressure ventilation or mechanical ventilation; whether or not pain medication was provided, including type of pain medication (opioid, NSAIDs, acetaminophen, other); number of red blood cell transfusions given; and whether or not exchange transfusion was necessary. Demographics include age, race, and sex. SCD related medical information includes number of previous episodes of ACS, current administration of outpatient hydroxyurea, and prior DVT or PE. General medical information includes history of myocardial infarction; chronic lung disease, defined as a documented baseline arterial oxygen saturation less than 90% and/or home supplemental oxygen requirement; previous stroke; and current or former smoker.

Prespecified feasibility criteria are as follows: the ability to enroll potential study participants, which includes the timely notification of hospitalized patients with ACS, the capacity to consent eligible individuals, and the ability to appropriately randomize screened patients within 24 hours of diagnosis, all of which should occur at a frequency greater than or equal to 80%; inclusion and exclusion criteria that does not exclude potential study participants at a frequency greater than or equal to 20%; the proper administration of the study drug at a frequency greater than or equal to 90%; and the ability to completely and accurately collect clinical data of interest at frequency greater than or equal to 90%. The final aim of our pilot study is to provide preliminary data, with respect to treatment effect and variance, for future sample size calculations given the lack of existing data to help guide this process.

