4.6 Adverse Event Reporting

All adverse events (AE) experienced by study subjects are to be recorded on the CRF, regardless of the severity of the event or its relationship to study treatment. The AE reporting procedures are based on the CTCAE system, volume 4.03, 2010. Subjects will report any symptoms to the investigator, research staff, inpatient nursing staff, or treating physician. [name] will determine if symptoms qualify as an AE or SAE with confirmation by [name]. AEs will be classified as mild (does not interfere with routine activities), moderate (interferes somewhat with routine activities), or severe (impossible to perform routine activities). The following algorithm will be used to assess the causality of all AEs:

- **Not related:** The event can readily be explained by factors not involving UFH, and a temporal relationship with UFH does not exist.
- **Possibly related:** A clinical event, including laboratory test abnormality, with a reasonable time sequence to administration of UFH but which could also be explained by concurrent disease or other drugs or chemicals. Information on drug withdrawal may be lacking or unclear.
- **Probably related:** The temporal relationship between the administration of UFH is compelling, and the event cannot be explained by the subject's medical condition or other therapies.
- **Related:** The event follows a reasonable temporal sequence from the administration of UFH, follows a known or suspected response pattern to UFH, is confirmed by improvement upon stopping UFH, and reappears upon repeated exposure to UFH.

The investigator will follow up all AEs, regardless of severity, until satisfactory resolution. All subjects experiencing AEs will be monitored until symptoms subside and any abnormal laboratory values have returned to baseline, or until there is a satisfactory explanation for the changes observed, or until death, in which case a full pathologist's report will be supplied, if possible. Withdrawal from the clinical study and therapeutic measures shall be at the discretion of the investigator. As required by the IRB, if there is a serious, unexpected or adverse event that is determined to be associated with UFH, it will be reported to the IRB within 24 hours. If the event is not serious, unexpected or related to UFH, it will be reported within 5 days. All events must be assessed to determine the following:

- If the event meets the criteria for an SAE.

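### The transfusion outcome leaves out units given for heparin bleeding, which in practice lowers only Arm A's count, and the major-bleeding definition does not tie the hemoglobin fall or the units to the bleed

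*Combined protocol and SAP*

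**What the plan says.** **Transfusion outcome.** Section 3.3 (Data Collection and Statistical Considerations) makes the number of packed red cell units received between randomisation and study completion a secondary clinical outcome. It then removes any unit given because of proven or suspected bleeding from UFH. The same section lists the transfusion data to be collected daily: "number of red blood cell transfusions given; and whether or not exchange transfusion was necessary". Section 4.4, under potential benefits, names fewer transfusions among the gains UFH might bring.

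**Background transfusion.** Section 3.2 makes red cell transfusion a routine part of ACS care in both arms and adds exchange transfusion in severe disease.

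**Bleeding grades.** Section 4.4 states: "Bleeding may be major, defined as a decrease in hemoglobin 2 grams per deciliter or more; transfusion of 2 or more units" of red cells, or bleeding in a critical organ. The remaining category is residual: "Minor bleeding is defined as all bleeding episodes that do not meet criteria for major bleeding". The consequences of the higher grade are fixed: "The presence of major bleeding will result in the permanent discontinuation of UFH". Section 3.1 adds: "In the event of major bleeding, the anticoagulation effects of heparin will be reversed with protamine sulfate". For a minor bleed, stopping UFH is left to the investigator. Under Section 4.5, a major bleed associated with UFH is also handled as a serious adverse event and reviewed by the safety committee.

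**The concern.** The outcome rule works in one direction. UFH is the Arm A treatment, so units can be attributed to UFH haemorrhage, and removed, essentially only there. The person attributing them knows the assignment, and suspicion is enough. A harm of the drug is thereby taken out of an outcome on which the drug is expected to look better. The pilot's stated purpose includes giving preliminary treatment effects and variances for a larger trial, so the rule could be carried forward.

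The bleeding definition has a different problem. Two transfused units are a weak marker of bleeding severity where transfusion is routine, and hemoglobin can fall in sickle cell disease through hemolysis. If neither criterion has to be linked to the bleed, a trivial bleed in a patient transfused for ACS can be graded major. That patient would lose study drug permanently and receive protamine, whose risks listed in Section 4.4 include hypotension and, rarely, anaphylaxis. Two investigators could also grade the same event differently.

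**Working it through.** The plan gives no figure to reproduce here: N = 20 is stated to rest on clinical considerations, and the analysis is descriptive.

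**1. Transfusion outcome**

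Input: 10 patients per arm (Section 4.2). The Arm A mean is total counted units divided by 10, so leaving out *k* units lowers it by *k*/10.

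- *k* = 1: 1/10 = 0.1 unit
- *k* = 4, for example one patient transfused 4 units for a bleed: 4/10 = 0.4 unit

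Arm B's count is unchanged, so the difference between arms moves by the same amount, in favour of UFH. The documents give no expected number of units and no standard deviation, so this shift cannot be expressed as a share of a plausible effect.

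The qualifier *in practice* is needed because Section 3.2 allows clinically indicated anticoagulation during the study. An Arm B patient could therefore in principle receive heparin.

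**2. Bleeding definition: the text**

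- Section 4.4 takes bleeding as its subject, so a bleed must be present. It does not say that the bleed must produce the fall or be the reason for the units, and it gives no time window.
- Elsewhere the plan does state attribution. Section 3.3 separates units by reason for the transfusion outcome. The allergy paragraph of Section 4.4 requires that symptoms be thought due to UFH.
- Section 4.5 (association with UFH) and Section 4.6 (causality scale) link the event to the drug. They do not link the units or the hemoglobin fall to the bleed.

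**3. Bleeding definition: illustration of frequency**

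Let *m* be the chance that a UFH patient has a bleed. Let *b* be the chance of 2 or more background units or an unrelated 2 g/dL fall, taken as independent of the bleed. Then *p* = *m* × *b*, the expected number of upgraded bleeds is 10*p*, and P(at least one) = 1 − (1 − *p*)^10.

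The only bleeding figure in the documents is in Section 4.4: "The risk of bleeding with intravenous UFH in acute VTE is less than 3" per cent. It is used as *m* = 3%. The values *m* = 1% and 10%, all values of *b*, and independence are assumptions.

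| *m* | *b* | *p* | Expected in 10 | P(at least one) |
|---|---|---|---|---|
| 1% | 20% | 0.002 | 0.02 | 2% |
| 1% | 50% | 0.005 | 0.05 | 5% |
| 1% | 70% | 0.007 | 0.07 | 7% |
| 3% | 20% | 0.006 | 0.06 | 6% |
| 3% | 50% | 0.015 | 0.15 | 14% |
| 3% | 70% | 0.021 | 0.21 | 19% |
| 10% | 20% | 0.02 | 0.2 | 18% |
| 10% | 50% | 0.05 | 0.5 | 40% |
| 10% | 70% | 0.07 | 0.7 | 52% |

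At the cited 3%, the chance that no Arm A patient is affected is 81% to 94%. The 10% rows show how far the answer depends on a bleed rate that the documents do not give for ACS.

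**The case against.** **On the outcome.** The exclusion is prespecified and can be defended as tying the outcome to transfusion for ACS, with bleeding captured separately as an adverse event. Section 3.3 also collects the number of transfusions without that exclusion, so a total could be reported anyway. Both points are fair. They make the repair cheap, but the outcome as defined is still one-sided.

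**On the definition.** A clinician would often infer that the fall and the units must come from the bleed, and the attribution required elsewhere supports that reading. A rule that errs towards stopping therapeutic heparin after a real bleed is also defensible, since anticoagulation in ACS has not been studied. These arguments reduce the weight of the point. They do not supply the missing words in a rule with mandatory consequences.

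**Stronger readings that the documents do not support:**

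- *Routine transfusion alone triggers the stopping rule.* It does not, because a bleed must be present.
- *Section 4.6 contradicts Section 4.4.* Section 4.6 says: "Withdrawal from the clinical study and therapeutic measures shall be at the discretion of the investigator". That is a general adverse-event clause, and stopping UFH is not withdrawal from the study. The specific stopping rule naturally governs.
- *The reason for transfusion is not recorded.* This would be inferred from a summary list. The CRF is not in the documents, and the Section 3.3 outcome could not be derived without the reason.
- *Arm B safety data are missing.* Section 4.6 says: "All adverse events (AE) experienced by study subjects are to be recorded on the CRF, regardless of the severity of the event". Section 3.3 limits the safety evaluation to UFH recipients, but whether to tabulate adverse events by arm is a separate question and adds no weight here.

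**Conclusion.** The point holds at modest size. The firmer part is the transfusion outcome: a stated rule removes units by unblinded judgement after randomisation and in practice can only lower Arm A's count, by 0.1 in the mean per unit removed. This rests only on the text and on 10 patients in the arm. The number of units that would be removed is unknown, so nothing here shows that the outcome will be materially distorted.

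The second part is a gap in wording. Confidence is high that the causal link is not stated. How often a minor bleed would be upgraded cannot be derived from the documents. With 10 UFH patients it is probably low: 0.06 to 0.21 expected cases at the cited acute-VTE figure, given the assumed *b* and independence. Neither part undermines a descriptive pilot, but both are worth settling before the definitions pass to a larger trial.

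**What to change.** 1. **Section 3.3.** Make total red cell units after randomisation, in both arms, the transfusion outcome. Report haemorrhage-attributed units on a separate line. State whether exchange units count towards the total, since exchange is recorded separately. The total needs no attribution, and the separate line keeps what the exclusion was meant to show. Cost: one or two sentences, using data already collected.

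2. **Section 4.4.** Define a bleed as major if it causes a hemoglobin fall of 2 g/dL or more, or leads to 2 or more units given for that bleed (not for ACS or exchange), or is in a critical organ. Treat doubtful cases as bleeding-related. Confirm that the CRF holds the indication for each transfusion, and add that field if it does not. Cost: one or two sentences and at most one CRF field. The downside is a slightly narrower stopping rule that relies on open-label attribution and could delay stopping. The default for doubtful cases limits that risk, at the price of keeping some over-grading.

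3. **Optional and separate.** Tabulate adverse events by arm from the records already kept. This needs one extra table column and no added blood draws or visits.
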